Vocal cord cyst is a fluid-filled sac inside the vocal cord, with 2 subtypes: 1) Epidermoid cyst due to epithelial inclusion 2) Mucous retention cyst due to glandular ductal obstruction. Vocal cord cysts typically do not resolve with voice therapy, and are traditionally excised with microlaryngeal surgery with microflap technique or marsupialization. ^(6,7) In our previous RCT study, subgroup analysis did not show a significant difference of vocal cord cyst recurrence in both TNLS and MLS group. However, our cohort had a higher overall vocal cord cyst recurrence rate (13.8%) compared to historic cohort rate of 2.2-8.7%^(5, 8), which may be accounted by that our vocal cord cysts were ablated and marsupialized instead of removed in the TNLS group. Nevertheless, a recent case series by Gao and colleagues showed a good functional outcome of awake KTP-laser marsupialization in selected cases. ⁹ A larger cohort is warranted to compare TNLS to MLS for vocal cord cyst. Therefore, our authors would like to conduct a randomized controlled trial to compare tradition MLS surgery to TNLS, with hypothesis that TNLS would be non-inferior to traditional microlaryngeal surgery in benign laryngeal lesions, and with its additional benefits on minimization of anesthetic risks and hospital expenses, hopefully to expand its further application.

Methodology

Study setting

This is a prospective, single-cluster randomized controlled trial conducted at two tertiary referral hospitals (Prince of Wales Hospital and Alice Ho Miu Ling Nethersole Hospital, NTEC) in Hong Kong to compare the clinical and functional outcomes of office-based TNLS to traditional microlaryngeal surgery under general anesthesia for vocal cord cysts.

Eligibility criteria

All consecutive patients with vocal cord cysts interested in operative management will be screened for eligibility.

Inclusion criteria

Patients who are (i) older than 18-year-old; (ii) able to independently provide consent; and (iii) able to tolerate flexible laryngoscopy would be recruited.

Exclusion criteria

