2. Complete head and neck physical examination
3. Flexible laryngoscopy for confirmation of diagnosis, with photo documentation of site and size (in relative to length of vocal cord in full abduction)

Diagnosis would be explained to patients, and management options of conservative, microlaryngeal surgery under general anesthesia, and TNLS with their pros and cons would be discussed. Patient information sheet and informed consent are provided to facilitate the

process. Should the patient decide to participate in the study, consent of the study would be signed in the same clinic session. Patient would be informed of his randomized treatment group, and consent of the surgery would be also signed in the same section. Participation is voluntary and any study subject can decide to withdraw at any time of the study period. Upon study withdrawal, the patient will continue to receive standard treatment according to disease status.

In addition to above mentioned assessments, patient would also be assessed in a multidisciplinary voice clinic undergoing a detailed voice assessment co-organized with speech language pathologist, including Voice-Handicap Index (VHI-30), perceptual evaluation of voice, acoustic voice analysis, aerodynamic measures and laryngeal imaging.

Failure of study intervention

When patients cannot tolerate the allocated intervention, for example patients randomized to MLS group but contraindicated to general anesthesia, or patients randomized to TNLS but cannot tolerate transnasal laser surgery due to discomfort or anxiety, can crossover to other study arm. Outcomes would be analyzed by intention-to-treat principle.

Follow-up schedule

All patients would have follow-up in a multi-disciplinary voice clinic on post-op 2 weeks, 6 weeks, 3 months, 6 months and 1 year. During the postoperative follow-ups, patients are required to fill in a questionnaire and undergo voice assessments as mentioned above.

Primary outcome

The primary outcome was to compare the pre- and post-operative Voice-Handicap Index (VHI-30) of TNLS and MLS groups. The VHI-30 is a 30-item self-administered questionnaire, which has been shown to be a reliable measure for voice treatment outcome.^(10,11) It consists of three subscales, namely physical, functional and emotional. It provides an overall measurement of a person's vocal function and how it influences a person's everyday functioning and experience.

Secondary outcomes

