The secondary outcomes included other voice-related outcomes (i.e. perceptual analysis, acoustic voice analysis, aerodynamic measure, visual analog scale (VAS) on voice quality), procedure-oriented outcomes, patient-oriented outcomes and hospital costs. Perceptual evaluation of voice using the GBRAS scale, in which patients would be required to produce sustained vowel and connected speech voice samples. Two experienced speech-language pathologists blinded to the patient's information would rate the audio recordings. For acoustic voice analysis, it would be conducted using PRATT program with parameters including

jitter, shimmer, noise-to-harmonic ratio measures and cepstral peak performance. For aerodynamic measure, maximal phonation time (MPT) would be measured by instructing patients to phonate /a:/ sound for as long as possible after maximal inspiration, at a spontaneous, comfortable pitch and loudness level, for three consequent trials. In VAS, patients would be asked to self-rate their voice quality on a visual analog scale of 0 (best) to 10 (worst). Videostroboscopy would be conducted on all patients to identify any anatomical and physiological changes, which included presence of laryngeal pathology, vocal fold closure pattern, and mucosal wave pattern.

Procedure-oriented outcomes include operation time, completeness of lesion removal, complications in Clavien-Dindo classification, length of hospital stay, disease recurrence rate, and reoperation.

Patient-oriented outcomes included peri-operative throat, nose, and overall discomfort in visual analogue scale, a 10-point scale with 0 (least uncomfortable) to 10 (most uncomfortable).

Medical costs of both interventions would be also calculated respectively, including costs for inpatient hospital stay, medical staff, operating theater and consumables.

Sample size calculation

Power calculation demonstrated that with a sample size of 21 per group, a two-arm study has a power of 80% to demonstrate a non-inferiority margin 7 absolute score, with one-sided significance of 0.05 regarding the primary outcome parameter, i.e. VHI-30. The calculation was based on published data from Misono et al.¹² in which a VHI-30 score over 16 was determined as a minimal important difference. Assuming a 20% drop-out rate, at least 54 patients were required, with 27 patients in each arm.

Participant timeline

TIMEPOINT	D1	Allocation	Post-allocation		Close-out

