	Pre-op assessment	Intra-operative	Immediate post-operative	FU at 2w, 6w, 3mo, 6mo, 1y	
Enrolment					
Eligibility screen	X				
Informed consent	X				
Randomization					
MLS		X			
TNLS		X			
Assessment					
Demographics	X				
	X				
	X				
	X				
	X				
	X				
Disease					
Type of lesion	X				
Site of lesion	X				
Size of lesion	X				
FL / Videostroboscopy	X		X		X
Anaesthetic assessment					
ASA	X				
Functional assessment					
VHI30	X				X
Other secondary voice-related outcomes (MPT, Acoustic analysis etc)	X				X
Procedural data					
Operation time		X		X	
Peri-op tolerance scale		X		X	
Peri-op pain score		X		X	
Post-operative outcome					
LOS			X		
Residual lesion			X		X
Complications			X		X
Recurrence					X
Reoperation					X
Pathology					X

Randomization

Patients are randomized to receive either MLS under general anesthesia or TNLS under local anesthesia. Block randomization is used to ensure equal distribution between two treatment arms. To avoid selection bias, the blocking mechanism is designed by a third party not involved in the study, and is not disclosed to investigators. Randomization is only performed on the day of recruitment, which the recruiter shall contact the third party for the result randomized treatment group. Both the patients and the laryngologists cannot be blinded due to the nature of operation.

Statistical method

All outcome measurements will be analyzed with an intention-to-treat principle. Independent samples t-test will be used for parametric continuous variables; Mann-Whitney U test will be used for non-parametric continuous variables; chi-square test will be used for categorical variables. A p-value less than 0.05 will be considered to be statistically significant. All statistical analysis will be performed using SPSS version 26.0.

Data monitoring and confidentiality

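### The primary outcome does not say which of five post-operative VHI-30 assessments, or what summary of them, is held against the margin of 7, nor whether the quantity is the score or its change

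*Protocol*

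**What the plan says.** The Primary outcome section of the Protocol defines the endpoint in one sentence: "The primary outcome was to compare the pre- and post-operative Voice-Handicap Index (VHI-30) of TNLS and MLS groups". The rest of that section describes the questionnaire.

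The recruitment and pre-operative assessment section makes VHI-30 part of the voice clinic assessment. The Follow-up schedule then repeats that assessment: "All patients would have follow-up in a multi-disciplinary voice clinic on post-op 2 weeks, 6 weeks, 3 months, 6 months and 1 year", and at these visits "patients are required to fill in a questionnaire and undergo voice assessments as mentioned above". The word post-operative in the primary outcome therefore covers five measurements.

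The Sample size calculation, which arrives at 21 evaluable patients in each arm, states that "a two-arm study has a power of 80% to demonstrate a non-inferiority margin 7 absolute score". The test is one-sided at the 0.05 level, and the endpoint is identified only by the name of the questionnaire. On losses to follow-up the section adds: "Assuming a 20% drop-out rate, at least 54 patients were required, with 27 patients in each arm". It gives no visit and no standard deviation (SD).

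The Statistical method section assigns tests by type of variable, for example "Independent samples t-test will be used for parametric continuous variables", and names neither a visit nor a summary over visits. The Randomization section says that neither patients nor laryngologists can be blinded.

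**The concern.** A non-inferiority verdict needs one decision rule stated in advance. Here the instrument, the two arms and the margin are fixed, but the visit and the quantity are not. If TNLS meets the margin at some visits and misses it at others, the plan does not say what is concluded. The choice could then be made after the data are seen, in an unblinded trial with a self-reported outcome, where it would be hard to defend.

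The visits also answer different questions. Two weeks reflects early healing. One year covers the period in which a recurrence could affect the voice. Recurrence is the Background's own worry: it notes a higher cyst recurrence rate in the previous trial, "which may be accounted by that our vocal cord cysts were ablated and marsupialized instead of removed in the TNLS group". A 20% drop-out allowance also cannot be judged without knowing which visit it describes.

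A second ambiguity lies in the wording pre- and post-operative. It can mean a comparison of post-operative scores or of changes from baseline. Randomisation makes the expected difference between arms the same for both. The SD is generally not the same, so the power at 21 per group differs, and so will the estimate if the arms differ at baseline by chance.

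**Working it through.** **1. The plan's own figures.** Inputs from Sample size calculation: margin 7, one-sided 0.05, power 80%, 21 per group, drop-out 20%.

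- Drop-out: 21 / (1 − 0.20) = 26.25, rounded up to 27 per arm, 54 in total. This reproduces exactly.
- The 21 cannot be derived forwards, because no SD is stated. Solving n = 2 × (2.486 × SD / 7)² for SD, where 2.486 is 1.645 + 0.842 before rounding and the true difference is 0, gives SD = 7 × √(21/2) / 2.486 = 9.12 (8.97 with the t distribution). The Protocol does not say which visit, or whether score or change, such an SD would describe.

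**2. Can the visits disagree?** Illustration under assumptions that the Protocol does not supply: no true difference, 80% power at each visit, and five test statistics with equal pairwise correlation ρ. Each statistic has mean 2.486 and critical value 1.645. Conditioning on a shared normal factor u with density φ:

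- P(all five meet the margin) = ∫ φ(u) Φ((0.842 + √ρ u)/√(1 − ρ))⁵ du
- P(at least one meets it) = 1 − ∫ φ(u) Φ((−0.842 + √ρ u)/√(1 − ρ))⁵ du
- P(visits disagree) = P(at least one) − P(all)

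| ρ | At least one | All five | Disagree |
|---|---|---|---|
| 0.5 | 0.976 | 0.513 | 0.464 |
| 0.7 | 0.948 | 0.590 | 0.358 |
| 0.9 | 0.893 | 0.687 | 0.206 |

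Differences are taken before rounding. If the correlation instead decays with visit order (first-order autoregressive, 1,000,000 simulated trials), disagreement is 0.540, 0.442 and 0.272.

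**3. What a pre-stated rule would give in the same setting.**

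- One named visit: error 5%, power 80%.
- Average of the five visits: variance factor (1 + 4ρ)/5 = 0.60, 0.76, 0.92. Power = Φ(2.486/√factor − 1.645) = 0.941, 0.886, 0.828, with error 5%.
- Non-inferiority required at every visit: error no more than 5%, power 0.513, 0.590, 0.687 (the all-five column above).

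**4. Score or change.** Assume an SD of 9.1 at baseline and at the deciding visit, with correlation r between them. The change has SD 9.1 × √(2(1 − r)). The score adjusted for baseline has residual SD 9.1 × √(1 − r²). Putting these into the formula of step 1:

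| r | Post-operative score | Change | Baseline-adjusted |
|---|---|---|---|
| 0 | 21 | 42 | 21 |
| 0.3 | 21 | 30 | 20 |
| 0.5 | 21 | 21 | 16 |
| 0.7 | 21 | 13 | 11 |

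Entries are evaluable patients per group. The choice of quantity alone moves the requirement from 13 to 42 over this range.

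**The case against.** A statistical analysis plan may exist, and a model, a repeated-measures method or a hierarchy of visits could properly be set there. That answers much of any complaint about the Statistical method section. It does not answer the point about Primary outcome and Sample size calculation: the time point is part of the endpoint's definition, and the Protocol has already sized the trial on that endpoint.

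The timeline table might seem to supply the visit, because one VHI-30 mark appears to fall under close-out. Its columns may have shifted in extraction, and the Follow-up schedule has voice assessments at every visit. Even taken literally, a schedule of assessments does not make a visit decisive.

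The disagreement rates depend on assumptions. Equal power at every visit needs equal SDs and equal numbers evaluable, while losses normally accumulate by 1 year. The rates show that conflict is plausible and are not a forecast for this trial.

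Three stronger readings are tempting and are not supported:

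- *The type I error is inflated.* Success at any of five visits would carry an error above 5%, but the Protocol does not adopt that rule, so no such rate can be attributed to it.
- *The design figures are tied to nothing.* They are tied to VHI-30 and to a two-arm non-inferiority comparison. Only the visit or summary and the quantity are missing.
- *The sample size is wrong.* It is consistent with an SD of about 9.1. The unstated SD is a separate gap, which naming a visit would not close.

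Nor must the remedy be a single visit or an average. A rule requiring every visit, or a multiplicity-adjusted rule, would also control error if stated beforehand.

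**Conclusion.** The point holds in this form: the Protocol fixes instrument, arms and margin, but not the visit, the summary or other rule that decides non-inferiority, and not whether score or change is compared with 7. One margin, one error rate, one power and one drop-out allowance are therefore attached to up to five possible comparisons.

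The size can only be illustrated. Under the assumptions of equal correlation, no true difference and 80% power per visit, the visits would give conflicting verdicts in roughly one trial in five (correlation 0.9) to nearly one in two (correlation 0.5). Certainty that the definition is missing is high. Certainty about those percentages is low, since no correlation or SD is given. This should be corrected before outcome data are seen. It does not show that 54 patients are too few or that any stated figure contradicts another.

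**What to change.** Before any outcome data are seen, name one primary comparison in Primary outcome. For example: *The primary endpoint is total VHI-30 at 1 year after surgery, compared between groups with adjustment for pre-operative VHI-30; VHI-30 at the four earlier visits is secondary.* A pre-specified average over named visits would serve equally. One year fits the Background's concern about recurrence, but the choice is the sponsor's.

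State whether the margin of 7 applies to the post-operative score or to change. Adjusting for the pre-operative score is recommended because it settles this: with that covariate in a linear model, the estimated difference between groups is the same whether score or change is analysed. If adopted, it needs a matching line in Statistical method.

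In Sample size calculation, say that the margin, power and drop-out refer to the named comparison. Stating its SD there would close the separate gap at the same time.

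The cost is one sentence in each of two sections and one line in a third. No visits or data are added, and the step from 21 to 27 per arm is unchanged. Whether 21 itself stands depends on the SD of the named comparison. The downsides are that the claim rests on one comparison, that a late visit will have more drop-out, and that an average can mask a late divergence between the arms.

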Patients who are (i) under 18-year-old; (ii) unable to independently give an informed consent; (iii) unable to tolerate flexible laryngoscopy; (iv) allergic to local anesthesia; (v) had unfavorable anatomy such as prolapsing epiglottis precluding adequate visualization, extensive lesions and an expected difficult operation as judged by the surgeons; and (vi) with pathologies other than vocal cord cyst would be excluded from the study.

Study intervention

The active comparator is traditional microlaryngeal surgery under general anesthesia, which is the standard surgical care for vocal cord cyst at our institution. The experimental intervention would be awake transnasal laser-assisted surgery under local anesthesia, carried out in minor operation theater as a day-case basis in ENT ambulatory center.

Microlaryngeal surgery (MLS)

For traditional MLS under general anesthesia, the patient is admitted on the same day morning of the surgery with prior outpatient anesthetist assessment, or one day earlier to receive inpatient anesthesia assessment in special cases. The patient will be kept fast according to anesthetist assessment before surgery begins. After general anesthesia and intubation with microlaryngeal tube, the patient would be positioned on head-ring support for better alignment and access to glottis. After insertion of teeth guard, a laryngoscope will be inserted transorally under direct vision, and suspended with chest table support. Vocal cord cysts are visualized with microscope, and removed with microsurgery instruments with microflap technique and sent for routine section. Hemostasis is ascertained, then the laryngoscope is removed carefully under direct vision and injuries to pharyngeal walls, tongue base, teeth, lips and temporomandibular joints are checked. After the surgery, the patient is kept nil-by-mouth until fully awake, and is discharged on same day or the next day depending on the post-operative recovery. Patient will be discharged with voice rest for 3 days and prescription of Pantoprazole 40mg daily 4 weeks and Paracetamol as needed.

Awake transnasal laser-assisted surgery (TNLS)

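### Two hospitals take part, but the stated blocking balances only the arm totals, so hospital mix can differ between arms by chance: a minor, cheaply avoided loss of precision

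*Protocol*

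**What the plan says.** Under Study setting, the protocol describes a "single-cluster randomized controlled trial conducted at two tertiary referral hospitals". Under Randomization it states that "Block randomization is used to ensure equal distribution between two treatment arms". That section adds that "the blocking mechanism is designed by a third party not involved in the study, and is not disclosed to investigators", and that on the day of recruitment "the recruiter shall contact the third party for the result randomized treatment group". It names no stratification factor, and it does not mention hospital as something the recruiter reports when asking for an allocation.

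Under Statistical method, "Independent samples t-test will be used for parametric continuous variables", with a Mann-Whitney U test and a chi-square test for other types of variable. None of these contains a hospital term.

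Under Sample size calculation, the plan has 21 evaluable patients per arm, a non-inferiority margin of 7 VHI-30 points, and 27 per arm (54 in total) after allowing for 20% drop-out.

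**The concern.** Blocking on one common list keeps the number of patients per arm close to equal. It does nothing to keep each hospital's patients evenly divided between the arms. With 54 patients, the split of a hospital's patients can be visibly uneven by chance alone.

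If outcomes differ by hospital, an uneven split moves the observed arm difference in one direction or the other. VHI-30 is the primary outcome; length of stay, operation time and cost could plausibly depend more on the site. As stated, the plan handles hospital neither at allocation nor in the analysis. A later analysis plan could add a hospital term, but it could not stratify an allocation already made, so the allocation half of the point belongs in the protocol.

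**Working it through.** **Inputs from the protocol.** Two hospitals (Study setting); 21 evaluable per arm, 80% power, one-sided 0.05, margin 7, 20% drop-out, 27 per arm (Sample size calculation); block randomisation with no named stratum (Randomization).

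**Inputs assumed.** The number of patients from the smaller hospital (18 of 54, varied below) and the gap between hospital means (5 VHI-30 points). The protocol gives neither.

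**1. The plan's own figure.** 21 / (1 − 0.20) = 26.25, rounded up to 27 per arm and 54 in total. This agrees.

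**2. Imbalance with one common list.** Let k be the number of the 18 smaller-hospital patients who fall in one arm. With 27 per arm fixed, k is approximately hypergeometric with mean 9.

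- Variance of k = 27 × (18/54) × (36/54) × (54 − 27)/(54 − 1) = 3.06, so the SD is 1.75.
- Difference in hospital mix between arms = 2(k − 9)/27. Its SD is 2 × 1.75/27 = 13.0 percentage points; its mean absolute value is 10.1 points.
- A 7:11 split is a difference of 2 × 2/27 = 14.8 points. P(7:11 or worse) = 0.387.
- A 6:12 split is a difference of 2 × 3/27 = 22.2 points. P(6:12 or worse) = 0.148. This counts both directions, so it is about 0.07 towards each arm.

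**3. Other hospital shares.**

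| Patients from smaller hospital | SD of difference in mix | Mean absolute difference | P(k at least 3 from its mean) |
|---|---|---|---|
| 14 | 12.0 points | 9.3 points | 0.119 |
| 18 | 13.0 points | 10.1 points | 0.148 |
| 22 | 13.5 points | 10.5 points | 0.166 |

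At an equal split (27 from each hospital) the mean absolute difference is 11.1 points. If one hospital supplied 49 of the 54, it would be 6.7 points.

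**4. One list against separate lists.** This was simulated with permuted blocks of 4 or 6 (assumed sizes), N = 54, 20,000 runs per setting, and one hospital supplying 50% to 80% of patients.

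- One common list: mean absolute difference in mix 8.5 to 10.8 points; a difference of 20 points or more in 6% to 13% of runs.
- Separate list per hospital: mean absolute difference 1.6 to 2.5 points; a difference of 10 points or more in at most 0.1% of runs.

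**5. Effect on the VHI-30 difference.** Shift = difference in mix × gap between hospital means. With a gap of 5 points:

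- mean absolute imbalance: 0.101 × 5 = 0.5 points (7% of the margin);
- one SD of imbalance: 0.130 × 5 = 0.65 points (9%);
- 6:12 split: 0.222 × 5 = 1.1 points (16%).

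The shift is proportional to the gap, so a 10-point gap would double each figure.

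**6. Scale against sampling error.** The protocol states no SD. The value implied by 21 per arm is 7 / [(1.645 + 0.842) × √(2/21)] = 9.1, which gives a standard error of the arm difference of 9.12 × √(2/21) = 2.8. At a 5-point gap, one SD of hospital imbalance is 0.65/2.8 = 0.23 of that standard error.

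**The case against.** The strongest reply is that nothing here is an error. Blocked randomisation without strata is valid, and chance imbalance in any prognostic factor is part of the sampling error that the t-test and its confidence interval already allow for. This stands, and it is why the point is one of precision and is minor.

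Several further objections also carry weight.

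- The protocol says the trial is carried out at two hospitals, not outright that both recruit. It calls the trial single-cluster and refers in the singular to its institution, out-patient clinic and voice clinic. If one clinic recruits everyone, a recruiting-hospital stratum would do nothing.
- The block design is withheld from investigators, so separate hospital lists are not strictly excluded. None is stated, however, and the only stated aim is balance between arms.
- A hospital term in the model is commonly left to the analysis plan, which is not shown. Its absence alone would not be a finding.
- The gap between hospitals is assumed. A 10-point gap would exceed the whole implied patient SD of 9.1. If VHI-30 is analysed as change from baseline, only a hospital difference in improvement would matter.

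A reader might infer two stronger claims that the protocol does not support. The first is that TNLS, being "carried out in minor operation theater as a day-case basis in ENT ambulatory center", is tied to one site, so that hospital differences fall directly on the arm comparison. The protocol does not name that site. If there is only one, the difference in facility is part of the treatment contrast, and stratifying by recruiting hospital could not remove it. The second is that a hospital imbalance could not be separated from a treatment effect. If hospital is recorded, it can be tabulated and adjusted for.

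**Conclusion.** The point holds as a minor one. The stated allocation controls arm totals only, and the listed tests do not adjust for hospital, so an avoidable chance imbalance in hospital mix is left in a 54-patient trial. With 18 patients from the smaller hospital, the typical imbalance is about 10 percentage points, and a 6:12 split or worse has probability 0.15. With a 5-point hospital gap, the typical shift is 0.5 to 0.65 VHI-30 points, and about 1.1 points at 6:12, against a margin of 7.

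The probabilities rest on the assumed hospital share but change little between 14 and 22 patients. The shifts rest on an assumed gap for which the protocol gives no figure. The 6:12 case is a tail result, not the expected one. The conclusion also depends on both hospitals recruiting. The case for acting is that the remedy costs almost nothing, not that the damage would be large.

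**What to change.** State in Randomization whether both hospitals recruit. If they do, have the third party hold a separate permuted-block list for each recruiting hospital, and have the recruiter give the hospital when requesting an allocation. Vary the block sizes and keep them undisclosed, because the trial is open-label and a fixed size could let recruiters predict the end of a block. Include hospital as a factor in the between-arm VHI-30 comparison, for example in a linear model in place of the plain t-test.

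If hospital lists already exist, or only one hospital recruits, one sentence saying so settles the point.

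Cost: two lists instead of one and one extra model term, using the third-party arrangement already in place, with no additional patients. The downside is that each hospital's list may end in an incomplete block, so arm totals may differ by a few patients, and the hospital term uses one degree of freedom.

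### The named tests for continuous outcomes do not adjust for the pre-operative VHI-30, so a valid comparison gives up precision that the planned data could supply

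*Protocol*

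**What the plan says.** - **Statistical method.** "Independent samples t-test will be used for parametric continuous variables"; "Mann-Whitney U test will be used for non-parametric continuous variables". No covariate or baseline adjustment is mentioned here or elsewhere in the Protocol.
- **Primary outcome.** "The primary outcome was to compare the pre- and post-operative Voice-Handicap Index (VHI-30) of TNLS and MLS groups". The text does not say whether the post-operative score or the change is compared.
- **Recruitment and pre-operative assessment.** Every patient has a voice-clinic assessment "including Voice-Handicap Index (VHI-30), perceptual evaluation of voice, acoustic voice analysis, aerodynamic measures and laryngeal imaging". The participant timeline also marks VHI-30 pre-operatively.
- **Follow-up schedule.** "All patients would have follow-up in a multi-disciplinary voice clinic on post-op 2 weeks, 6 weeks, 3 months, 6 months and 1 year". The Protocol does not name one of these five visits as primary.
- **Sample size calculation.** "with a sample size of 21 per group, a two-arm study has a power of 80% to demonstrate a non-inferiority margin 7 absolute score", at one-sided 0.05. Neither an SD nor a correlation is given.
- **Order of baseline and allocation.** "Randomization is only performed on the day of recruitment" (Randomization), and at that clinic session "Patient would be informed of his randomized treatment group, and consent of the surgery would be also signed in the same section" (Recruitment and pre-operative assessment). The voice-clinic assessment is described after this, with no order relative to disclosure.

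**The concern.** The Protocol plans a baseline measurement of its primary scale and then names a test that makes poor use of it. A t-test on post-operative scores ignores the baseline. A t-test on change fixes the baseline slope at 1, which is efficient only if r × SDpost/SDpre is close to 1. ANCOVA estimates the slope from the data.

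The trial is small and has to exclude a 7-point margin, so the width of the confidence interval decides whether a truly non-inferior TNLS passes. A wider interval than necessary makes a false failure more likely. Chance baseline imbalance is part of this same loss of precision, not a further problem.

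The timing of the baseline bears on the remedy. VHI-30 is self-administered and patients are not blinded, so a baseline completed after the patient knows the allocation could be influenced by it and would be a poor covariate.

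**Working it through.** **Inputs.** From the Protocol: 21 evaluable per arm, margin 7, one-sided 0.05, power 80%. Assumed: true difference 0; SD back-solved; r (within-arm correlation of pre- and post-operative VHI-30) of 0.3, 0.5 and 0.6; higher VHI-30 is worse.

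**1. The Protocol's own figure.** Without an SD, the 21 per arm cannot be reproduced independently, only inverted.
- Normal approximation: SD = 7/(1.645 + 0.842) × √(21/2) = 9.12.
- Noncentral t, 40 df: SD = 8.97 for 80% power. I use 9, which gives 79.7%.
- The dropout step reproduces: 21/0.8 = 26.25, hence 27 per arm and 54 in total.

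**2. Validity of the named test.** In 100,000 simulated trials (21 per arm, r = 0.5), one-sided type I error was 0.0496 for the t-test on post-operative scores and 0.0485 for the t-test on change. The test is valid.

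**3. Variance of ANCOVA relative to the t-test (large-sample).**
- Against post-operative scores: 1 − r² = 0.91, 0.75, 0.64, so 9%, 25%, 36% less.
- Against change, equal SDs: (1 + r)/2 = 0.65, 0.75, 0.80, so 35%, 25%, 20% less.
- Against change, with k = SDpost/SDpre: k²(1 − r²)/(k² + 1 − 2rk). At r = 0.5 this is 0.465, 0.75, 0.964 and 1.00 for k = 0.7, 1, 1.5 and 2.

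Estimating the slope multiplies the ANCOVA variance by 1 + 1/(2n − 4) = 39/38 in expectation.

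**4. Power and interval width.** Noncentral t, 39 df for ANCOVA. The unadjusted half-width is t(0.95, 40) × 9 × √(2/21) = 1.684 × 2.777 = 4.68 points; this is the distance from the estimate to the one-sided 95% limit.

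| | r = 0.3 | r = 0.5 | r = 0.6 |
|---|---|---|---|
| Unadjusted power | 80% | 80% | 80% |
| ANCOVA, if SD 9 is the post-score SD | 83% | 89% | 93% |
| – with factor 39/38 | 82% | 88% | 92% |
| – half-width (without factor) | 4.46 | 4.05 | 3.74 |
| ANCOVA, if SD 9 is the change SD (equal pre/post SDs) | 92% | 89% | 87% |
| – with factor 39/38 | 92% | 88% | 86% |
| – half-width (without factor) | 3.77 | 4.05 | 4.19 |

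**5. Where the gain stops.** Against a post-score test, break-even is 1 − r² = 38/39, so r = √(1 − 38/39) = 0.16. At r = 0, ANCOVA gives 78.8% against 79.7% unadjusted.

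**6. The same loss seen as imbalance.** With a baseline SD also of 9, one standard error of the baseline difference is 9 × √(2/21) = 2.78 points. With equal SDs, r times this (0.8, 1.4, 1.7 points) reaches a post-score estimate, and (1 − r) times this (1.9, 1.4, 1.1 points) reaches a change-score estimate.

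**The case against.** The strongest reply is that this is a preference. The test is valid, the sample size section assumes no covariate, so design and analysis agree, and adjustment is often left to the SAP. It is true that nothing here falls short of the planned 80%. But the Protocol does not leave the method open: it names unadjusted tests for continuous outcomes, which include the primary. An SAP that adjusted for baseline would depart from that text.

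Second, the size of the gain cannot be known from the Protocol. That stands. SD, r and the SD ratio are all assumed, and the chosen r values lie where ANCOVA gains; the full range runs from a slight loss to a substantial gain. If the primary comparison is a change score, the baseline is already partly used. At r = 0.5 with SDpost/SDpre of 1.5 or 2, the factor 39/38 turns the ratios 0.964 and 1.00 into 0.99 and 1.026, which is no gain or a small loss.

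Third, the timeline places VHI-30 in the first, pre-operative column. This does not settle the order, because consent, randomization and disclosure fall on the recruitment day as well.

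Two limits also stand. The point does not reach operation time, length of stay or cost, which have no baseline. The Mann-Whitney route was not quantified.

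**Conclusion.** The concern holds as a point of efficiency. The Protocol names a valid but usually less precise comparison although the covariate is already planned. Under SD 9, true difference 0 and r = 0.5, the chance of missing the margin when TNLS is truly equivalent falls from about 20% to about 12%, and the confidence limit moves about 0.6 points closer to the estimate (4.68 to 4.05, before the slope factor). That the test is unadjusted, and the usual direction of the effect, are firm. The size is not, since it rests on an SD and a correlation that the Protocol does not state. This should be changed, but it does not threaten the trial's validity.

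**What to change.** In Statistical method, replace the unadjusted test for the primary outcome as follows:

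- Define the primary estimate as the TNLS minus MLS difference in VHI-30 at one visit, named from the five scheduled.
- Estimate it by ANCOVA with treatment and pre-operative VHI-30, or as the contrast at that same visit from a baseline-adjusted repeated-measures model. Fix one of the two in advance, and say what will be done if the residuals are clearly non-normal.
- Compare the one-sided 95% upper limit with 7 (taking higher VHI-30 as worse), in line with the one-sided 0.05 in the sample size section.
- State that the covariate is a VHI-30 completed before the patient is told the allocation.
- Use the same approach for continuous secondary voice measures that have a pre-operative value.

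The cost is wording and one degree of freedom, and the method is available in SPSS. No new data are needed, provided the pre-operative VHI-30 is completed before disclosure.
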